10.3 Study Termination

Although the Sponsor has every intention of completing the study, the Sponsor reserves the right to discontinue the study at any time for clinical or administrative reasons.

The end of the study is defined as the date on which the last subject completes the final end of study assessment.

10.4 Final Report

Whether the study is completed or prematurely terminated, the Sponsor will ensure that the clinical study report is prepared and provided to the regulatory agency as required by the applicable regulatory requirement(s). The Sponsor will also ensure that the clinical study report in marketing applications meet the standards of the ICH harmonized tripartite guideline E3: Structure and content of clinical study reports.

Where required by applicable regulatory requirements, an Investigator signatory will be identified for the approval of the clinical study report. The Investigator will be provided reasonable access to statistical tables, figures, and relevant reports and will have the opportunity to review the complete study results.

Upon completion of the clinical study report, the Sponsor will provide the Investigator with the full summary of the study results. The Investigator is encouraged to share the summary results with the study subjects, as appropriate. The study results will be posted on publicly available clinical trial registers.

12 APPENDICES

12.1 Appendix 1: Chronic Kidney Disease Classification Criteria

This study uses the 2009 CKD-EPI creatinine equation,¹⁶ which is recommended by the KDIGO Clinical Practice Guidelines for Management of Chronic Kidney Disease.

The CKD-EPI equation is:

$$eGFR = 141 \times \min\left(\frac{Scr}{\kappa}, 1\right)^\alpha \times \max\left(\frac{Scr}{\kappa}, 1\right)^{-1.209} \times 0.993^{Age} \times 1.018 \text{ (if female)} \times 1.159 \text{ (if black)},$$

where Scr is serum creatinine, κ is 0.7 for females and 0.9 for males, α is -0.329 for females and -0.411 for males, min indicates the minimum of Scr/ κ or 1, and max indicates the maximum of Scr/ κ or 1.

12.2 Appendix 2: Schedule of Assessments

Table 12-1 Schedule of Assessments

Visit type:		Screening ¹⁷	Admit ¹⁷	In-CRU	In-CRU	Discharge after AM Assessments		PK Visit in AM		PK Visit in AM; Admit for PM dose	In-CRU	Discharge after PK Collection and Assessments	PK Collection ¹⁸	End of Study Visit
Procedure:	Study Day:	-44 to -3 or -2	-2 or -1	-1	1	2	3	4	5	6	7	8	9-11	35 ±2
Informed Consent		X												
Demographics		X												
Medical History		X												
Serum/Urine Pregnancy Test ^{1,2}		X	X											X
FSH ³		X												
Height/Weight/BMI		X												X
Inclusion/Exclusion		X												
Previous Medications ¹		X	X											
Concomitant Medications ⁴		X		X	X	X		X		X	X	X	X	X
Clinical Lab Evaluations ⁵		X		X	X	X					X	X		X
Serum Creatinine ⁶		X		X	X	X					X	X		X
Electrocardiogram ⁷		X			X							X		
Vital Signs ⁸		X		X	X	X		X		X	X	X		X
Physical Examinations ^{1,9}		X	X									X		X
Adverse Events ¹⁰								X						
Daily Fluid Intake ¹¹				X	X	X (AM only)					X	X (AM only)		
Administer Dose in-CRU ¹²					AM PM	AM		AM		AM PM	AM PM			
Self-Administer Dose ¹²						PM	AM PM	PM	AM PM					
PK Blood Samples ¹³					X	X		X		X	X	X	X	
Urine Osmolality ¹⁴				X	X	X					X	X		
Daily Urine Output ¹⁵				X	X	X (AM only)					X	X (AM only)		
Tolerability Questionnaire						X					X			
Plasma Copeptin ¹⁶				X		X					X			X
TKV and LV (by MRI)				X							X			X

Abbreviations: BMI= body mass index, CRU = clinical research unit, EOS = end of study, FSH = follicle-stimulating hormone, MRI = magnetic resonance imaging, PK = pharmacokinetic, Preg. = pregnancy, TKV = total kidney volume, LV = liver volume.

- ¹ Assessments will be performed on Day -1 or Day -2 for subjects admitted to CRU on Day -2.
- ² Serum pregnancy test to be performed at Screening; Urine pregnancy test to be performed at Day -2 or Day -1 and at End of Study.
- ³ Postmenopausal subjects with a urine pregnancy result outside the post-menopausal range or an indeterminate pregnancy test will undergo additional testing with FSH if necessary based on Investigator discretion to confirm postmenopausal status prior to study enrollment.
- ⁴ Includes over the counter medications.
- ⁵ Clinical labs: hematology, clinical chemistry (including liver function), and urinalysis at approximately the same time of day (in the morning and, on dosing days, before the lixivaptan dose). The list of analytes is shown in [Table 6-1](#). Lab tests that need to be repeated during Screening may be obtained through the services of an at-home nursing service provided by the Sponsor.
- ⁶ Serum creatinine will be measured as part of the clinical laboratory assessment.
- ⁷ 12-lead ECG at Screening, Day 1 pre-dose, and prior to discharge from clinic on Day 8. Electrocardiograms to be obtained following 5 minutes rest in supine or semi-recumbent position. The same position must be used throughout the study for a given subject.
- ⁸ Vital signs will be measured following 5 minutes rest in a seated position. Systolic and diastolic blood pressure, pulse rate, respiratory rate, body temperature will be measured at the following time points: prior to Day -1 procedures, prior to discharge from CRU on Day 8, and at the End of Study visit. In addition, blood pressure and pulse rate will also be measured before each administration of study medication in the CRU.
- ⁹ Complete physical examination at Screening, and prior to discharge on Day 8. Brief physical examination on Day -2 or Day -1. Symptom-directed physical examinations as needed.
- ¹⁰ Adverse events and SAEs that are related to study participation (e.g., protocol-mandated intervention) will be recorded from the time the subject signs the informed consent form until exit from the study. All other AEs and SAEs will be recorded from the first dose of lixivaptan until exit from the study.
- ¹¹ Record daily fluid intake on Day -1, Day 1 and Day 7. On Day -1, measurement will begin 24 hours before the expected time of first study medication on Day 1 AM. On Day 1 and Day 7, measurements will begin immediately before the AM dose and will continue for 24 hours into the morning of Day 2 and Day 8, respectively.
- ¹² Subjects will take study medication in the AM and PM for 7 days. Subjects will be asked to record each dose of the study product taken on an outpatient basis in the Study Dosing Diary. Subjects will be asked to bring the Study Dosing Diary together with their unused study product at each visit to the CRU.
- ¹³ PK blood collection timepoints:
Day 1: 0, 1, 2, 4, 6, 9, 10, 11, 12, 14, and 16 hours post AM dose. The collections at 0 and 10 hours are immediately before the AM and PM doses, respectively;
Day 2, 4 and 6: 0 hours (immediately before AM dose);
Day 7: 0, 1, 2, 4, 6, 9, 10, 11, 12, 14, and 16 hours post AM dose. The collections at 0 and 10 hours are immediately before the AM and PM doses, respectively;
Day 8: 0 hours (corresponding to 24 hours after AM dose on Day 7) and 10 hours (corresponding to 24 hours after PM dose on Day 7);
Day 9: 48 hours after PM dose on Day 7;
Day 11: 96 hours after PM dose on Day 7.
- ¹⁴ Urine will be collected for determination of spot urine osmolality and urine specific gravity at the following timepoints:
Day -1: 0 (start), 1, 2, 4, 6, 9, 10, 11, 12, and 14 hours.

Day 1: 0, 1, 2, 4, 6, 9, 10, 11, 12, and 14 hours post AM dose. The collections at 0 and 10 hours are immediately before the AM and PM doses, respectively;

Day 2: 0 hours (immediately before AM dose on Day 2, corresponding to 24 hours after AM dose on Day 1).

Day 7: 0, 1, 2, 4, 6, 9, 10, 11, 12, and 14 hours post AM dose. The collections at 0 and 10 hours are immediately before the AM and PM doses, respectively;

Day 8: 0 hours (corresponding to 24 hours after AM dose on Day 7).

Note: Subject may not be able to void at all timepoints - see [Section 6.1.7](#). For all voids, the volume (mL) and the date and time of void will be recorded.

- ¹⁵ Record daily urine output on Day -1, Day 1 and Day 7. On Day -1, measurement will begin 24 hours before the expected time of first study medication on Day 1 AM. On Day 1 and Day 7, measurements will begin immediately before the AM dose and will continue for 24 hours into the morning of Day 2 and Day 8, respectively.
- ¹⁶ Blood samples for determination of plasma copeptin will be taken at approximately the same time of day (in the morning and, on dosing days, before the lixivaptan dose).
- ¹⁷ Subjects will be admitted to the CRU in the evening of Day -2 or in the morning of Day -1. For subjects admitted to the CRU on Day -2, the Screening period will be until Day -3. For subjects admitted to the CRU on Day -1, the Screening period will be until Day -2.
- ¹⁸ Three PK sampling points are contemplated after patients are discharged from the CRU on Day 8 (Day 8 PM, Day 9 PM, Day 11 PM). Patients may return to the site for these PK sample collections. Alternatively, if patients are not able to return to the CRU after discharge, they may utilize an at-home nursing service provided by the Sponsor. If a patient does not return to the site for PK sample collection after discharge on Day 8, but has the blood drawn by an at-home nursing service, this will not be considered a protocol deviation.

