2.2 Study Endpoints

2.2.1 Primary Endpoints

- The following PK parameters will be calculated using noncompartmental methods, whenever possible, based on the plasma concentrations of lixivaptan and its major metabolites (WAY-141624, WAY-138451, and WAY-138758), for lixivaptan and each metabolite: maximum observed plasma drug concentration (C_{max}), time to reach maximum plasma concentration (t_{max}), area under the plasma concentration-time curve (AUC) from time 0 until the last quantifiable concentration (AUC_{0-t}), AUC extrapolated to infinity (AUC_{0-inf}), terminal elimination phase half-life ($t_{1/2}$), apparent terminal elimination rate constant (λ_z), total body clearance (CL/F; lixivaptan only), and volume of distribution (V_z/F ; lixivaptan only).
- The safety and tolerability of lixivaptan will be assessed through evaluation of physical examination findings, vital signs, 12-lead electrocardiograms (ECG), clinical laboratory findings (clinical chemistry, hematology and urinalysis), assessments of adverse events (AE) and a questionnaire assessing aquaretic tolerability (symptom burden of nocturia, urgency, frequency).

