6.1.2 Physical Examinations and Medical History

Complete physical examinations will include, at a minimum, general appearance and assessment of the following systems: skin, head, ears, eyes, and throat, respiratory system, cardiovascular system, gastrointestinal system, neurologic system, blood and lymphatic systems, and the musculoskeletal system. A licensed physician or qualified designee will conduct the examinations.

Brief physical examinations include, at a minimum, assessment of the following systems: skin, head, eyes, and throat, chest and heart auscultation, abdominal examination, neurologic condition (i.e., alert and oriented x3; not including cranial nerves), and edema and hydration assessment. A licensed physician or qualified designee will conduct the examinations.

Physical examinations may be performed at various unscheduled time points if deemed necessary by the Investigator. Symptom-directed physical examinations will be performed as appropriate for subjects experiencing AEs.

Medical history and demographic data, including initials, sex, age, race, and ethnicity will be recorded at the timepoints specified in the study schedule of assessments ([Table 12-1](#)).

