### 16.6. PHYSICAL EXAMINATION

All physical examination findings, including non-scheduled symptom-directed examination results, will be listed individually for each scheduled timepoint, including specification of any abnormalities observed. Incidences of physical examination results (Normal, Abnormal NCS, Abnormal CS) for every visit, as well as a shift table summarizing the changes in physical examination assessments (Normal, Abnormal NCS, Abnormal CS) from baseline to EOS will be provided, using counts and percentages for each cohort. New abnormalities occurring after administration of study medication will be recorded as adverse events.

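### The Day 8 physical examination need not include the oedema and hydration item required at baseline, and the SAP shift table omits Day 8: a minor gap in one primary safety component

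*Protocol*

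**What the plan says.** Physical examination findings are the first item in the safety part of the primary endpoints (protocol 2.2.1) and are listed again in the primary estimand of the Non-PK/PD SAP (7.2).

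Protocol 6.1.2 defines two scheduled types of examination. The complete one is a floor list of body systems: "Complete physical examinations will include, at a minimum, general appearance and assessment of the following systems: skin", and so on to the musculoskeletal system. Oedema and hydration are not on it. The brief examination has its own floor list, which ends with "neurologic condition (i.e., alert and oriented x3; not including cranial nerves), and edema and hydration assessment".

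Table 12-1 marks examinations at Screening, at admission, on Day 8 and at End of Study. Footnote 9 assigns the types: "Complete physical examination at Screening, and prior to discharge on Day 8. Brief physical examination on Day -2 or Day -1". It assigns none to End of Study.

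For analysis, protocol 7.7.3 plans a summary of changes from baseline in examination findings and does not restrict it to one visit. Non-PK/PD SAP 16.6 plans a listing by timepoint with any abnormality specified, incidences at every visit, and "a shift table summarizing the changes in physical examination assessments (Normal, Abnormal NCS, Abnormal CS) from baseline to EOS". Section 3.3 of that SAP reports no meaningful departure from the protocol's analyses.

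**The concern.** The drug is expected to cause water loss. Protocol 5.9 asks subjects to aim for 4 to 5 litres of fluid a day while taking it. Volume status is thus a finding for which the physical examination has particular value, yet the plan requires it only before the first dose.

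Two separate things follow for the examination endpoint. First, baseline and Day 8 do not have the same minimum content. A subject whose only baseline abnormality was oedema could be recorded as normal on Day 8 because nobody was required to look. Second, the only within-subject table compares baseline with a visit about four weeks off drug. An absence of shifts there describes the state after washout and says little about change on treatment.

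**Working it through.** No power or sample-size calculation is involved. The check sets the content, timing and analysis passages side by side.

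**Timing.**
- Day 8, hour 0, is 24 h after the Day 7 morning dose (Table 12-1, footnote 13). The evening dose follows the morning dose by 10 h (protocol 3.1). So the Day 8 morning is 24 − 10 = 14 h after the last dose.
- End of Study is Day 35 ± 2 and the last dose is on Day 7. So 33 − 7 = 26 to 37 − 7 = 30 days off drug.

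**Content by visit** (protocol 6.1.2, Table 12-1 and footnote 9).

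| Scheduled examination | Relation to dosing | Type stated | Oedema/hydration in minimum content | Role in SAP shift table |
|---|---|---|---|---|
| Screening | before first dose | complete | no | baseline only if it is the last pre-dose examination |
| Day -2 or Day -1 | before first dose | brief | yes | normally baseline (Non-PK/PD SAP 6.3) |
| Day 8 | about 14 h after last dose | complete | no | none |
| End of Study | 26 to 30 days after last dose | not stated | cannot be determined | endpoint |

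Of 4 scheduled examinations, 1 is explicitly brief, and it precedes dosing. The number of scheduled examinations on Days 1 to 8 that must record oedema and hydration is 0 of 1. Protocol 4.2.1 makes early-termination procedures the same as those before the Day 8 discharge, so subjects who withdraw under that section inherit the same content.

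**Analysis outputs in Non-PK/PD SAP 16.6.**
- Listing by timepoint: includes Day 8.
- Incidence at every visit: includes Day 8.
- Shift table: omits Day 8.

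So 2 of 3 outputs carry the Day 8 result. The one that does not is the only one that tabulates within-subject change, and it is narrower than protocol 7.7.3.

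**The two parts are independent.** The shift table uses three overall classes, and 16.6 mentions no breakdown by body system. A Day 8 block would show within-subject change on treatment but would not isolate hydration. Adding the item to the Day 8 examination would supply the finding but not the tabulated shift. Each needs its own correction.

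**The case against.** The case that little is lost is strong, and most of it stands.

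- **Day 8 is analysed.** It appears in the incidence table and in the listing with the abnormality named. With 8 subjects per cohort and no planned safety comparisons, a reader can pair each subject's baseline and Day 8 result from the listing.
- **New findings have another route.** SAP 16.6 also says that abnormalities newly arising after dosing are recorded as adverse events, and treatment-emergent events are tabulated by cohort in 16.1.2. That is an on-treatment, within-subject comparison for anything that is found. It does not help if the item is not examined.
- **A minimum list is not a ceiling.** Nothing stops an examiner noting dehydration on Day 8 under general appearance or skin. Section 6.1.2 adds: "Symptom-directed physical examinations will be performed as appropriate for subjects experiencing AEs". These passages permit the finding; they do not require it.
- **Hydration on drug is measured elsewhere.** Fluid intake and urine output over 24 h are recorded on Days -1, 1 and 7. Blood pressure and pulse are taken before each dose given in the unit, chemistry is drawn on Days 2 and 7, and fluid balance is a named endpoint in PK/PD SAP 15.1. Protocol 5.9 also has the investigator assess fluid needs. These cover water balance well, though vital signs are seated only and weight is scheduled only at Screening and End of Study.

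A reader might infer that the trial has no on-drug assessment of hydration, or that the Day 8 examination goes unanalysed. The documents support neither. Nor do they say that the brief examination occurs only before dosing: the untyped End of Study examination could be brief. That would still be an off-drug finding.

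**Conclusion.** The point holds as a minor one, confined to the physical-examination component of the primary safety endpoint. Followed exactly, the plan compares a baseline examination that must include oedema and hydration with a Day 8 examination that need not, leaves the End of Study examination undefined, and tabulates within-subject shift only after 26 to 30 days off drug.

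This affects the planned content for all of the approximately 32 subjects. It threatens neither the overall safety assessment nor any other endpoint, because the remaining hydration data and the adverse-event route are intact. The conclusion assumes that sites work to the minimum lists as written, and that baseline is normally the Day -2 or Day -1 examination.

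**What to change.** 1. Reconcile protocol 6.1.2 with footnote 9 so that the Day 8 examination includes the oedema and hydration item recorded at baseline.
2. State in footnote 9 which type of examination is done at End of Study.
3. In Non-PK/PD SAP 16.6, add a baseline-to-Day 8 block to the shift table and keep the baseline-to-End of Study block. This also brings the SAP back into line with protocol 7.7.3.

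The cost is a phrase in 6.1.2 or footnote 9, about a minute at an examination already being performed, and one more block in an existing table. No visit is added.

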12.3 Appendix 3: Assessment Windows

Table 12-2 Assessment Windows

Procedure	Dosing Day	Window (units)
Lixivaptan PM dose	Day 1 – Day 7	In CRU: 10 hr ± 15 minutes after AM dose Self-Administered: 10 hr ± 1 hr after AM dose
	Assessment Day	
PK Blood Samples	Day 1, Day 2, Day 4, Day 6, Day 7, Day 8, Day 9, Day 11	- 60 minutes (predose Day 1) - 10 minutes (predose Day 7) ± 3 min (≤4 hr) ± 5 min (> 4 hr but ≤ 12 hr) ± 10 min (> 12 hr but ≤ 24 hr) ± 1 hr (> 24 hr but ≤ 48 hr) ± 2 hr (> 48)
Urine Osmolality and Urine Specific Gravity	Day 1-2, Day 7-8	Subjects will empty their bladders completely 15 ± 5 minutes prior to each scheduled collection, after which they will have 30 minutes to provide a spot urine sample. Subjects who will not be able to provide a sample within 30 minutes will be given an additional 30 minutes to do so and the different sampling time will be recorded.
Electrocardiogram	Screening, Day 1, Day 8	- 60 minutes (predose), ± 30 minutes (postdose)
Vital Signs	Screening, Day -1, Day 1, Day 2, Day 4, Day 6, Day 7, Day 8, Day 35	- 60 minutes (predose), ± 30 minutes (postdose)
Clinical Laboratory Samples	Screening, Day -1, Day 2, Day 7, Day 35	- 60 minutes (predose Day 2 and Day 7) In the morning on Day -1 and Day 35
Tolerability Questionnaire	Day 2, Day 7	Subjects will complete the questionnaire in the morning of Day 2, before discharge from the CRU, and in the morning of Day 7.
TKV and LV (MRI)	Baseline End of dosing End of study	Baseline: between Screening and Day -1 End of dosing: Day 7 or 8 or 9 End of study: Day 35 ± 2

Table abbreviations: hr = hours, PK= pharmacokinetic

Summary of Changes in the Conduct of the Study (from Section 9.8.1 of the Clinical Study Report, dated September 22, 2020)

Changes in the Conduct of the Study

There were 2 protocol versions that were not implemented or submitted to the IRB. Protocol versions 1 and 2 were marked final and dated 19 March 2018 but the version number 1.0 remained unchanged in the footer of both versions. Refer to Note to File (dated 23 February 2020) in Appendix 16.1.1 to distinguish between the 2 documents.

Protocol version 3 (dated 24 April 2018) was the first protocol version submitted to the IRBs and amended. There were 2 subsequent protocol amendments, versions 4 and 5, that were implemented after the first subject was enrolled. Copies of the protocol and protocol amendments are provided in Appendix 16.1.1. Brief summaries of the changes are outlined below.

Protocol version 4 (dated 09 January 2019) implemented the following changes:

- Clinically relevant changes that affected the type or frequency of protocol procedures, or the addition of information to the protocol that influenced clinical decision making or consent:
 - Increased eligible age to 65 years for inclusion in the study;
 - Provided flexibility in screening procedures;
 - Allowed the use of the low progesterone-releasing intrauterine device Mirena;
 - Limited hormonal contraception exclusion to estrogen-containing contraceptives. Progesterone-only contraceptives were allowed.
 - Allowed inclusion of subjects with elevated bilirubin due to Gilbert’s Syndrome at the discretion of the investigator.
 - Allowed inclusion of subjects with contraindications to or interference with MRI assessments provided they met all other inclusion criteria. Clarified that no MRI tests would be conducted on these subjects.
 - Added exclusion of subjects who showed signs of liver toxicity on tolvaptan therapy.
 - Clarified batch number of investigational product.
 - Clarified fluid intake recommendations before the first dose of study drug and while taking study drug.
 - Allowed supine position for ECGs provided that the same position was maintained for the same subject throughout the study.
 - Clarified nature of pregnancy test at EOS visit.
 - Added Day 11 to the Assessment Window table.
 - Clarified the appropriate time window for time values that were on the extremes of each time interval.
- Clarified text which included corrections of typos, text changes for consistency or other clarifications which did not affect clinical decision making or consent. These included deletion of mesylate, the counter-ion of fenoldopam from the exclusion criteria.

- Administrative changes, including changes of names or roles of companies or personnel and/or contact information. These changes did not affect clinical decision making or consent.

Protocol version 5 (dated 21 March 2019) implemented the following changes:

- Clinically relevant changes that affected the type or frequency of protocol procedures, or the addition of information to the protocol that influenced clinical decision making or consent:
 - Extended screening duration from 4 weeks to 6 weeks.
 - Increased study duration by the addition of 14 days to Screening.
 - Updated information on the status of the vasopressin V2 receptor antagonist tolvaptan (JYNARQUE®) in the US.
 - Provided flexibility to stop enrollment of CKD1 subjects in Cohorts 1 and 3 if sufficient experience with CKD2 subjects had not occurred.
 - Provided the use of a home nursing service to draw blood if repeat lab tests were needed during Screening.
 - Deleted amlodipine from the exclusion criteria and prohibited therapy as it was a CYP3A4 substrate and not an inhibitor.
 - As inhibition of CYP3A4 by lixivaptan might reduce metabolism of amlodipine, a dosing limit was added.
 - Increased the allowable upper limit of liver function test (LFT) results at Screening to $1.5 \times \text{ULN}$ based on the observation in the first 8 subjects treated with lixivaptan at 200 mg BID (highest dose) in this study that no significant LFT abnormalities had been detected. The highest values were $1.2 \times \text{ULN}$ for transaminases with no increase in total bilirubin.
 - Clarified that if a subject did not come back for visits after Day 8, it was not a protocol deviation if the blood was drawn only by the at-home nursing service.
- Clarified text which included corrections of typos, text changes for consistency or other clarifications. These changes did not affect clinical decision making or consent.
- Administrative changes, including changes of names or roles of companies or personnel and/or contact information. These changes did not affect clinical decision making or consent.

Study PA-102 Clinical Study Protocol version 5 dated March 21, 2019 Summary of Changes

This Summary of Changes document should be used in conjunction with the tracked-changes version of the clinical study protocol amendment. Page numbers reported herein refer to the **tracked-changes** version.

Administrative Changes

This section lists administrative changes, including changes of names or roles of companies or personnel and/or contact information. No changes listed here affect clinical decision making or consent.

Page	Section	Version 4 dated January 9, 2019	Version 5	Explanation
1	Title page	Version of Protocol: 4	Version of Protocol: 5	Clarifies protocol version
1	Title page	Date of protocol: January 9, 2019	Date of protocol: March 21, 2019	Updates protocol date
1	Title page	Sponsor Contact: [name] [name], BCPS Vice President, Clinical Development and Operations Design Space Inpharmatics, LLC [name] [contact]	Sponsor Contact: [name] Vice President, Clinical Operations Palladio Biosciences, Inc. [name] [name] [contact]	Updates Sponsor Contact name and contact information.
3	Protocol approval – Sponsor signature	Version of Protocol: 4	Version of Protocol: 5	Updates protocol version

Page	Section	Version 4 dated January 9, 2019	Version 5	Explanation
3	Protocol approval – Sponsor signature	Protocol date January 9, 2019	Protocol date March 21, 2019	Updates protocol date
3	Protocol approval – Sponsor signature	[name]. President & CEO Palladio Biosciences, Inc. [name] [name]	[name]. Chief Medical Officer Palladio Biosciences, Inc. [name] [name]	Change of responsibility to Chief Medical Officer
3	Protocol approval – Sponsor signature	Signature date January 9, 2019	Signature date March 21, 2019	Updates protocol date
11	Synopsis	Date of protocol: January 9, 2019	Date of protocol: March 21, 2019	Updates protocol date
All	Footnote	09-Jan-2019	21-Mar-2019	Updates protocol date
All	Footnote	Version 4	Version 5	Updates protocol version

Text Clarifications

This section lists corrections of typos, text changes for consistency or other clarifications. These changes do not affect clinical decision making or consent.

Page	Section	Version 4 dated January 9, 2019	Version 5	Explanation
11	Synopsis	Pharmacokinetic: Lixivaptan and lixivaptan metabolite (WAY-141624, WAY-138451, and WAY-138758) plasma concentrations will be tabulated and summarized using descriptive statistics (including sample size, arithmetic and geometric mean, standard deviation [SD], coefficient of variation [CV%], median, minimum, and maximum) for each Cohort. The PK parameters for lixivaptan and lixivaptan metabolites will be summarized for each Cohort.	Pharmacokinetic: Lixivaptan and lixivaptan metabolite (WAY-141624, WAY-138451, and WAY-138758) plasma concentrations will be tabulated and summarized using descriptive statistics (including sample size, arithmetic and geometric mean, standard deviation [SD], coefficient of variation [CV%], median, minimum, and maximum) for each Cohort. The PK parameters for lixivaptan and lixivaptan metabolites will be summarized for each Cohort.	Deletion of duplicate words
13	List of Abbreviations		REMS Risk Evaluation and Mitigation Strategy	Adds new abbreviation
35	5.8.1 Permitted Therapy	Allowed medications include those typically prescribed to treat ADPKD, CKD and their complications, with the exception of tolvaptan. These include angiotensin II receptor blockers (valsartan, candesartan, telmisartan, irbesartan) and angiotensin-converting enzyme inhibitors (enalapril, lisinopril).	Allowed medications include those typically prescribed to treat ADPKD, CKD and their complications, with the exception of tolvaptan. These include angiotensin II receptor blockers (e.g. , valsartan, candesartan, telmisartan, irbesartan) and angiotensin-converting enzyme inhibitors (e.g. , enalapril, lisinopril).	Added “e.g.”, to show these are examples and not a complete list.

Clinically-relevant Changes

This section describes changes that affect the type or frequency of protocol procedures, or the addition of information to the protocol that influences clinical decision making or consent.

Page	Section	Version 4 dated January 9, 2019	Version 5	Comments
10	Synopsis	Screening Duration : 28 days (Day -30 through Day -3)	Screening Duration : 42 days (Day -44 through Day -3)	Extends the duration of Screening from 4 weeks to 6 weeks
10	Synopsis	Total Study Duration : 66 days	Total Study Duration : Up to 80 days	Study duration is increased by the addition of 14 days to Screening.
16	1.3 Overview of Available Therapies for ADPKD	As of the time of this document there are no drug therapies specifically approved in the US for the treatment of ADPKD.	In April 2018, the vasopressin V₂ receptor antagonist tolvaptan (JYNARQUE®) was approved in the US to slow kidney function decline in adults at risk of rapidly progressing ADPKD. However, because of the risk of serious liver injury, Jynarque is only available through a restricted distribution program under a Risk Evaluation and Mitigation Strategy (REMS).	Updates information on the status of Jynarque in the United States.
22	3.1 Study Design	For all subjects, this study includes a Screening period of 28 days (Day -30 through Day -3), i.e. up to 30 days prior to dosing on Day 1.	For all subjects, this study includes a Screening period of 42 days (Day -44 through Day -3), i.e. up to 44 days prior to dosing on Day 1.	Extends the duration of Screening from 4 weeks to 6 weeks.

Page	Section	Version 4 dated January 9, 2019	Version 5	Comments																								
23	3.1 Study Design, Table 3-1, footnote	
Table 3-1 Chronic Kidney Disease Classification Summary
 
  
 CKD Classification	Cohorts	N	eGFR*	
   
 CKD1 or CKD2**	1 and 3	16 (8 per cohort)	eGFR ≥ 60 mL/min/1.73 m²	
 
 CKD3	2 and 4	16 (8 per cohort)	eGFR ≥ 30 to < 60 mL/min/1.73 m²	
  
 
Abbreviations: CKD = chronic kidney disease, eGFR = estimated glomerular filtration rate, N = number of subjects. *eGFR is calculated by the 2009 Chronic Kidney Disease Epidemiology Collaboration (CKD-EPI) equation (Appendix 1).
	CKD Classification	Cohorts	N	eGFR*	CKD1 or CKD2**	1 and 3	16 (8 per cohort)	eGFR ≥ 60 mL/min/1.73 m ²	CKD3	2 and 4	16 (8 per cohort)	eGFR ≥ 30 to < 60 mL/min/1.73 m ²	
Table 3-2 Chronic Kidney Disease Classification Summary
 
  
 CKD Classification	Cohorts	N	eGFR*	
   
 CKD1 or CKD2**	1 and 3	16 (8 per cohort)	eGFR ≥ 60 mL/min/1.73 m²	
 
 CKD3	2 and 4	16 (8 per cohort)	eGFR ≥ 30 to < 60 mL/min/1.73 m²	
  
 
Abbreviations: CKD = chronic kidney disease, eGFR = estimated glomerular filtration rate, N = number of subjects. *eGFR is calculated by the 2009 Chronic Kidney Disease Epidemiology Collaboration (CKD-EPI) equation (Appendix 1). **At least 2 subjects with CKD1 or CKD2 will be included in 8 subjects assigned to Cohorts 1 and 3.
	CKD Classification	Cohorts	N	eGFR*	CKD1 or CKD2**	1 and 3	16 (8 per cohort)	eGFR ≥ 60 mL/min/1.73 m ²	CKD3	2 and 4	16 (8 per cohort)	eGFR ≥ 30 to < 60 mL/min/1.73 m ²	Provides for flexibility to stop enrollment of CKD1 subjects in Cohorts 1 and 3 if sufficient experience with CKD2 subjects has not occurred.
CKD Classification	Cohorts	N	eGFR*																									
CKD1 or CKD2**	1 and 3	16 (8 per cohort)	eGFR ≥ 60 mL/min/1.73 m ²																									
CKD3	2 and 4	16 (8 per cohort)	eGFR ≥ 30 to < 60 mL/min/1.73 m ²																									
CKD Classification	Cohorts	N	eGFR*																									
CKD1 or CKD2**	1 and 3	16 (8 per cohort)	eGFR ≥ 60 mL/min/1.73 m ²																									
CKD3	2 and 4	16 (8 per cohort)	eGFR ≥ 30 to < 60 mL/min/1.73 m ²																									
23	3.1 Study Design	Subjects may be allowed to re-screen or have repeat testing after agreement between the investigator and medical monitor.	Subjects may be allowed to re-screen or have repeat testing after agreement between the investigator and medical monitor. Lab tests that need to be repeated during Screening may be obtained through the services of an at-home nursing service provided by the Sponsor.	Provides for the use of a home nursing service to draw blood if repeat lab tests are needed during Screening.																								
27	4.1.2 = Exclusion criteria	6.Subjects who have taken, or are expected to be taking, strong or moderate CYP3A4 or CYP2C8 inhibitors (e.g. aprepitant, boceprevir, clarithromycin, chloramphenicol (not eye	6.Subjects who have taken, or are expected to be taking, strong or moderate CYP3A4 or CYP2C8 inhibitors (e.g. aprepitant, boceprevir, clarithromycin, chloramphenicol (not eye	Amlodipine is a CYP3A4 substrate and not an inhibitor. Thus, it has been deleted from this section.																								

Page	Section	Version 4 dated January 9, 2019	Version 5	Comments
		
drops), cimetidine, ciprofloxacin, clopidogrel, clotrimazole (if used orally), cobicistat and cobicistat-containing products, crizotinib, cyclosporine, danazol, deferasirox, diltiazem, dronedarone, erythromycin, fluconazole, fluvoxamine, gemfibrozil, HIV protease inhibitors, imatinib, isoniazid, itraconazole, josamycin, ketoconazole, nefazodone, posaconazole, quinupristin/dalfopristin, ritonavir and ritonavir-containing products, telaprevir, teriflunomide, tofisopam, troleandomycin, verapamil, voriconazole) within 14 days or 5 half-lives, whichever is longer, of dosing; or weak CYP3A4 or CYP2C8 inhibitors (e.g., amlodipine, chlorzoxazone, cilostazol, fosaprepitant, istradefylline, ivacaftor, lomitapide, ranitidine, ranolazine, tacrolimus, ticagrelor, trimethoprim) within 7 days or 5 half-lives, whichever is longer, from dosing. For weak CYP3A4 or CYP2C8 inhibitors, medications may be allowed in consultation with the Medical Monitor (MM).
	
drops), cimetidine, ciprofloxacin, clopidogrel, clotrimazole (if used orally), cobicistat and cobicistat-containing products, crizotinib, cyclosporine, danazol, deferasirox, diltiazem, dronedarone, erythromycin, fluconazole, fluvoxamine, gemfibrozil, HIV protease inhibitors, imatinib, isoniazid, itraconazole, josamycin, ketoconazole, nefazodone, posaconazole, quinupristin/dalfopristin, ritonavir and ritonavir-containing products, telaprevir, teriflunomide, tofisopam, troleandomycin, verapamil, voriconazole) within 14 days or 5 half-lives, whichever is longer, of dosing; or weak CYP3A4 or CYP2C8 inhibitors (e.g., amlodipine, chlorzoxazone, cilostazol, fosaprepitant, istradefylline, ivacaftor, lomitapide, ranitidine, ranolazine, tacrolimus, ticagrelor, trimethoprim) within 7 days or 5 half-lives, whichever is longer, from dosing. For weak CYP3A4 or CYP2C8 inhibitors, medications may be allowed in consultation with the Medical Monitor (MM).
	
28	4.1.2. – Exclusion criteria	15. Subjects with aspartate aminotransferase (AST), alanine aminotransferase (ALT), gamma-glutamyltransferase (GGT), alkaline phosphatase (ALP) or total bilirubin \geq 1.0 \times upper limit of normal (ULN) at Screening. Subjects with elevated	15. Subjects with aspartate aminotransferase (AST), alanine aminotransferase (ALT), gamma-glutamyltransferase (GGT), alkaline phosphatase (ALP) or total bilirubin $>$ 1.5 \times upper limit of normal (ULN) at Screening. Subjects with elevated	Increases the allowable upper limit of liver function test (LFT) results at Screening to 1.5 \times the upper limit of normal based on the observation in the first 8 subjects treated with

Page	Section	Version 4 dated January 9, 2019	Version 5	Comments
		bilirubin due to Gilbert's Syndrome may be allowed at the discretion of the Investigator.	bilirubin due to Gilbert's Syndrome may be allowed at the discretion of the Investigator.	lixivaptan at 200 mg BID (highest dose) in this study that no significant LFT abnormalities have been detected. The highest values were 1.2 times the upper limit of normal for transaminases with no increase in total bilirubin.
32	5.2 Blinding and Randomization	This is an open-label study and no blinding procedures will be used. Following enrollment, subjects will be centrally assigned to one of 4 cohorts depending on CKD status (Table 5 1) and based on a predetermined algorithm. The 200 mg BID dose cohorts will be enrolled first. At least 2 males or females will be included in the 8 subjects (i.e., can be up to a 25%/75% split of male/female or 75%/25% split of male/female) assigned to each cohort.	This is an open-label study and no blinding procedures will be used. Following enrollment, subjects will be centrally assigned to one of 4 cohorts depending on CKD status (Table 5 1) and based on a predetermined algorithm. The 200 mg BID dose cohorts will be enrolled first. At least 2 males or females will be included in the 8 subjects (i.e., can be up to a 25%/75% split of male/female or 75%/25% split of male/female) assigned to each cohort. Similarly, at least 2 subjects with CKD1 or CKD2 will be included in 8 subjects each assigned to Cohorts 1 and 3.	Provides for flexibility to stop enrollment of CKD1 subjects in Cohorts 1 and 3 if sufficient experience with CKD2 subjects has not occurred.
